5.5 Pharmacokinetic, Pharmacodynamic, and Other Biomarker Analyses

Analyses related to PK, PD, and biomarkers will be detailed in separate analysis plans.

5.6 Safety Analyses

The primary safety endpoint of the study is the proportion of subjects with intolerable Grade 2 or any \geq Grade 3 TEAEs within 24 weeks after randomization. The primary safety endpoint will be performed on the Per-Protocol Safety Analysis Set, Safety Analysis Set will be used for descriptive purpose. A sensitivity analysis for primary safety endpoint based on Per-Protocol Analysis Set 2 will also be performed. Other safety assessments include TEAEs, clinical laboratory evaluations, vital signs, electrocardiograms (ECGs), and echocardiogram or MUGA scan including left ventricular ejection fraction (LVEF). All safety analyses will be performed on the Safety Analysis Set. Some selected safety analyses will also be performed on Per-Protocol Safety Analysis Set.

5.6.1 Primary Safety Endpoint

If the boundary for the non-inferiority test on the primary efficacy endpoint ORR_{24w} is crossed, the following superiority test at 2-sided $\alpha=0.05$ on the primary safety endpoint (ie, the proportion of subjects with intolerable Grade 2 or any \geq Grade 3 TEAEs within 24 weeks after randomization) will be performed:

$$H_0: \Delta_{14mg-18mg} = 0$$

$$H_a: \Delta_{14mg-18mg} \neq 0$$

where $\Delta_{14mg-18mg}$ is the difference in the proportion of subjects with intolerable Grade 2 or any \geq Grade 3 TEAEs within 24 weeks after randomization between lenvatinib 14 mg and lenvatinib 18 mg arm.

The proportion of subjects with intolerable Grade 2 or any \geq Grade 3 TEAEs within 24 weeks after randomization will be tested using the CMH test at 2-sided $\alpha=0.05$, stratified by MSKCC prognostic group and prior PD-1/PD-L1 treatment from IxRS data.

At each interim analysis and the final analysis, if the non-inferiority boundary of the primary efficacy endpoint is crossed, the analysis of the primary safety endpoint will be performed on Per-Protocol Safety Analysis Set. The proportions will also be summarized on Safety Analysis Set for descriptive purpose. A sensitivity analysis on primary safety endpoint will be performed on Per-protocol Analysis Set 2.

A sensitivity analysis for the primary safety endpoint based on the stratification factors from CRF data in clinical database will also be performed on Per-Protocol Safety Analysis Set.

To explore homogeneity of treatment effect across centers/regions, a sensitivity analysis for the primary safety endpoint using logistic regression model with center/region along with stratification factors as covariates will be conducted to adjust center/region effect.

The summary of intolerable Grade 2 and \geq Grade 3 TEAEs by SOC and PT is specified in [Section 5.6.3.3](#).

5.6.2 Extent of Exposure

Extent of exposure to study treatment, study drug administered, and study drug modifications will be summarized and presented for each individual drug and overall. The dosing and treatment exposure for those 32 subjects who had received ≥ 2 incorrect lenvatinib doses due to IxRS issue will also be summarized and listed.

5.6.2.1 Extent of Exposure to Study Treatment

Treatment duration and the total number of treatment cycles will be summarized descriptively. The maximum number of treatment cycles for each subject is the largest cycle number in which a subject receives any non-zero dose of study drugs. The number and percentage of subjects treated within each cycle will also be summarized for each treatment arm.

Treatment duration will be summarized descriptively for each individual drug and overall. The dosing end date will be imputed to the analysis cutoff date if the subject is still on treatment at the time of the data cutoff, and the dose will be imputed with the last dose recorded in the database for that subject.

The duration of each individual drug in months will be calculated as $(\text{Date of the last non-zero dose} - \text{Date of the first non-zero dose} + 1)/30.4375$ for the specific drug, including drug interruption days. For overall treatment duration, it is defined as the duration between the earliest first dose start date of study drugs and the latest last dose end date of study drugs.

In this study, study drugs refer to lenvatinib 14 mg, lenvatinib 18 mg, and everolimus 5 mg.

5.6.2.2 Study Drug Administered

The total dose received per subject, dose intensity, and relative dose intensity will be summarized with descriptive statistics for each individual study drug.

For each individual study drug, the total dose per subject (mg) will be calculated as the sum of all doses that subject has received during the study. The dose intensity (mg/day) will be calculated as the total dose (mg) received during the study divided by the treatment duration of the specific drug (days). The relative dose intensity, which is defined as the ratio (%) of total dose received and total planned dose (ie, received dose as a percentage of planned dose), will be calculated as the dose intensity divided by the daily planned dose.

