5.2.7 Treatment Compliance

Records of treatment compliance for each subject will be kept during the study, including the Follow-up Period. Clinical research associates will review treatment compliance during investigational site visits and at the completion of the study. Received dose as percent of planned dose per subject (ie, relative dose intensity) will be summarized as described in [Section 5.6.2.2](#), no other analysis of treatment compliance is planned.

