The treatment difference in ORR_{24W} between lenvatinib 14 mg and lenvatinib 18 mg will also be estimated along with 90% CIs based on the asymptotic normal approximation.

If non-inferiority in ORR_{24W} is claimed, the superiority test at 2-sided $\alpha=0.05$ for the primary safety endpoint will be performed. The details are specified in Primary Safety Endpoint [Section](#)

5.6.1.

Sensitivity analyses of ORR_{24W} based on Full Analysis Set and Per-Protocol Analysis Set 2 will be performed in a similar manner as described above.

To explore homogeneity of treatment effect across centers/regions, a sensitivity analysis of ORR_{24W} using logistic regression model with center/region along with stratification factors as covariates will be conducted to adjust center/region effect.

Sensitivity analyses of ORR_{24W} based on the stratification factors from CRF data in clinical database will also be performed on Per-Protocol Analysis Set 1, Full Analysis Set and Per-Protocol Analysis Set 2.

For this study, for subjects in the lenvatinib 14 mg QD with everolimus 5 mg arm, lenvatinib dose should be escalated to 18 mg QD (with everolimus 5 mg) as long as there are no intolerable Grade 2 or any \geq Grade 3 TEAEs that require dose reductions in the first 28-day cycle. To evaluate any potential impact due to failing to up-titrate the doses for eligible subjects in the lenvatinib 14 mg QD with everolimus 5 mg arm, another sensitivity analysis may be performed on Per-Protocol Analysis Set 1 to exclude those subjects who should have been up-titrated by protocol but were actually not up-titrated by investigators, if the number of such cases in the lenvatinib 14 mg QD with everolimus 5 mg arm is deemed high (eg, $\geq 10\%$).

An analysis of ORR_{24W} based on the data prior to when the protocol was amended to open-label (from double-blinded) (ie, treatment assignments were unblinded to investigator sites on 14 July 2018) will be performed on Per-Protocol Analysis Set 1 and Per-Protocol Analysis Set 2 to check for consistency of study results before and after the protocol became un-blinded.

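### SAP 5.6.2.2 calculates relative dose intensity from a daily planned dose, but no fixed value is right for the 14-mg arm, where the plan steps up to 18 mg at Cycle 2

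*SAP*

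**What the plan says.** SAP 5.6.2.2 describes RDI in two ways. By definition it is a quantity "which is defined as the ratio (%) of total dose received and total planned dose". By calculation it "will be calculated as the dose intensity divided by the daily planned dose". The numerator of the calculation is set out just before: "The dose intensity (mg/day) will be calculated as the total dose (mg) received during the study divided by the treatment duration of the specific drug". Section 5.6.2.1 takes that duration from the first to the last non-zero dose "for the specific drug, including drug interruption days".

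The daily planned dose is not defined by arm or by cycle. The nearest text is in 5.6.2.1, where "study drugs refer to lenvatinib 14 mg, lenvatinib 18 mg, and everolimus 5 mg".

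The step-up is part of the plan for the 14-mg arm. SAP 5.4.1 says that "lenvatinib dose should be escalated to 18 mg QD (with everolimus 5 mg) as long as there are no intolerable Grade 2" or Grade 3-or-worse events needing a reduction in Cycle 1. SAP 3.2 repeats the rule. Protocol 7.3 and 9.4.5 place the 4-mg increase on Day 1 of Cycle 2 and describe it as required when the dose is tolerated. The 18-mg regimen has no planned increase.

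SAP 5.2.7 makes RDI the sole compliance summary: "no other analysis of treatment compliance is planned".

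**The concern.** Total received over total planned equals dose intensity over daily planned dose only when the same dose is planned every day. That holds for everolimus 5 mg and for the 18-mg arm. It fails for every 14-mg subject who is escalated or was eligible to be.

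The error therefore falls in one arm only, in a trial that compares two starting-dose regimens. Depending on the divisor chosen, the 14-mg arm can look over-dosed or under-dosed relative to the 18-mg arm when adherence is identical. With a divisor of 14 mg, real dose loss can also disappear. An eligible subject who was never escalated, the departure for which SAP 5.4.1 foresees a possible sensitivity analysis, would read 100%.

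**Working it through.** The documents state no RDI figure, so there is none to reproduce.

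**Inputs.** Cycle length is 28 days (SAP 3.2). The 14-mg arm's plan is 14 mg in Cycle 1, then 18 mg if the escalation rule is met and otherwise 14 mg (protocol 9.4.5; SAP 5.4.1). The 18-mg arm's plan is 18 mg throughout. The horizon used here is 24 weeks = 168 days. The share of the 14-mg arm that escalates is not given, so it is taken as *f* between 0 and 1.

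**Formulas.**
- As written: RDI = (mg received / days) / D, with D a fixed 14 or 18 mg.
- By the SAP's own definition: RDI = mg received / mg planned.

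**Planned dose over 24 weeks.**
- Escalated: 28 × 14 + 140 × 18 = 392 + 2520 = 2912 mg, which is 2912/168 = 17.33 mg/day.
- Properly kept at 14 mg: 168 × 14 = 2352 mg.

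**Individual subjects in the 14-mg arm.**

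| Subject | Received (mg) | Planned (mg) | D = 14 | D = 18 | Received/planned |
|---|---|---|---|---|---|
| Escalated, every dose taken | 2912 | 2912 | 123.8% | 96.3% | 100% |
| Properly kept at 14 mg, every dose taken | 2352 | 2352 | 100% | 77.8% | 100% |
| Eligible but not escalated | 2352 | 2912 | 100% | 77.8% | 80.8% |
| Escalated, then 14 mg from Cycle 3 | 2464 | 2912 | 104.8% | 81.5% | 84.6% |

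In the last row, 392 + 28 × 18 + 112 × 14 = 2464 mg. An 18-mg-arm subject who goes to 14 mg from Cycle 3 receives 56 × 18 + 112 × 14 = 2576 mg of 3024 planned, or 85.2%. Near-identical dose loss (84.6% and 85.2%) would read 104.8% and 85.2% if D = 14 were used.

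**Dependence on duration.** For a fully adherent escalated subject:
- 8 weeks: 896/56 = 16.00 mg/day, giving 114.3% (D = 14) or 88.9% (D = 18).
- 48 weeks: 5936/336 = 17.67 mg/day, giving 126.2% or 98.1%.
- Limit with D = 14: 18/14 = 128.6%.

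**Arm average at 24 weeks, everyone taking all of their own plan.**
- D = 14: 100(1 − *f*) + 123.8*f*. For *f* = 0, 0.25, 0.5, 0.75, 1 this is 100.0, 106.0, 111.9, 117.9, 123.8%.
- D = 18: 77.8(1 − *f*) + 96.3*f*. This is 77.8, 82.4, 87.0, 91.7, 96.3%.
- 18-mg arm: 100% in every case.

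If both arms take 80% of their own plan, the 14-mg arm reads 80.0–99.0% (D = 14) or 62.2–77.0% (D = 18), against 80.0% in the 18-mg arm.

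**The case against.** The strongest reply is that the SAP never says the divisor is one fixed number. The same sentence defines RDI through the total planned dose. If the daily planned dose is read as each subject's total planned dose divided by days on treatment, formula and definition agree and an adherent escalated subject scores 100%. SAP section 9 places programming rules in separate documents, which are not available here and may say exactly that. This stands as far as it goes: the intended quantity is clear from the definition, and the separate specification may be right. But the averaged reading appears nowhere in the SAP, and nothing in it makes the divisor change at Cycle 2.

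A reader might infer from the study-drug labels in 5.6.2.1 that 14 mg is the divisor, and hence that RDI in the 14-mg arm is inflated. The documents do not establish this. Those labels identify the study drugs in a section on treatment duration; they set no denominator rule. With 18 mg the error runs the other way, and it is larger for subjects who properly stay at 14 mg. The direction of the bias is therefore unknown. What holds is that neither constant fits both kinds of subject.

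It is also fair to say that RDI is a descriptive summary and not a listed endpoint, and that no between-arm test of it is planned.

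**Conclusion.** The point holds as a conflict between a definition and its calculation. Any fixed daily planned dose gives a wrong RDI for part of the 14-mg arm. At 24 weeks the error is +23.8 or −3.7 percentage points for a fully adherent escalated subject, and 0 or −22.2 points for one properly kept at 14 mg, with divisors of 14 and 18 mg respectively. The arm-level size depends on an escalation rate that the documents do not give. The ranges of 100–123.8% and 77.8–96.3% assume full adherence, 24 weeks on treatment for everyone, and any escalated share from 0 to 100%.

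Two larger conclusions should not be drawn. A reader might infer that exposure cannot be compared between the arms. That goes too far: 5.6.2.2 already summarizes total dose and dose intensity in mg/day, neither of which uses a planned dose, and 5.6.2.3 covers reductions and interruptions. A reader might also take RDI to be a main tolerability measure. The documents give that role to the primary safety endpoint in 5.6.1 and use RDI only as the compliance summary. The primary tests, alpha, power and sample size are untouched, so this is a minor correction.

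**What to change.** In SAP 5.6.2.2, replace the calculation with total dose received divided by the cumulative protocol-planned dose over the subject's treatment duration, keeping the duration in 5.6.2.1. For the 14-mg arm, count 14 mg per day through Cycle 1. From Cycle 2 Day 1 count the protocol's escalated level for subjects who met the existing escalation rule, and 14 mg for those who did not. State that toxicity-driven reductions and interruptions do not lower the planned dose, so that RDI still shows dose loss. An eligible subject left at 14 mg is then measured against the stepped plan. The 18-mg arm and everolimus are unchanged, and no dosing rule is altered.

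The cost is one derivation rule. Escalation eligibility has to be derived from adverse-event and dosing data, including whether a Cycle 1 event required a reduction. The optional up-titration sensitivity analysis in 5.4.1 already needs this, because eligible subjects who were not escalated must be counted to decide whether to run it. No extra mg/day table is needed, since that summary is already planned.

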5.6.2.3 Study Drug Dose Reductions and Interruptions

DOSE REDUCTIONS

Dose reduction refers to a situation that a dose level was reduced from the previous dose level without going back. Dose reduction could apply to any of the study drugs: lenvatinib 18 mg/day (could reduce to 14, 10, 8, and 4 mg/day), lenvatinib 14 mg/day (could reduce to 10, 8, and 4 mg/day), and everolimus (5 mg every day could reduce to 5 mg every other day).

DOSE INTERRUPTIONS

Dose interruption refers to a situation that a subject had a planned temporary break from taking the study drug for a short period (ie, interruption period). Dose interruption could apply to any of the study drugs.

Dose interruption only refers to the scenario that the dose levels or dosing frequencies before and after interruption period (defined as the period with dose=0) are the same. For example: 18 mg lenvatinib followed by 0 mg and followed by 18 mg lenvatinib; 5 mg everolimus every day followed by 0 mg followed by 5 mg everolimus every day. If the dose level after dose interruption period was reduced from the dose level before the interruption period, it should be counted as dose reduction and should not be counted as dose interruption. The following 2 scenarios are examples of dose reduction instead of dose interruption:

- (1) 18 mg lenvatinib followed by 0 mg followed by 14 mg lenvatinib;
- (2) 5 mg everolimus every day followed by 0 mg followed by 5 mg everolimus every other day;

Please note, for the 2 scenarios above, the period with dose=0 should be counted as dose reduction period and not dose interruption (ie, the dose reduction date should be the date of dose=0). If the subject discontinued from treatment permanently after dose interruption with dose=0, it should be counted as treatment discontinuation instead of dose interruption.

The number of subjects with dose reductions and dose interruptions for each individual study drug will be summarized. Number (ie, frequency) of dose reductions per subject will also be summarized.

Time to first dose reduction is defined as the time period from the first dose date to the date of first dose reduction, or the time period from the first dose date to the date of first dose interruption for those subjects who had dose interruption first and then followed by dose reduction. Time to first dose reduction will be derived and summarized descriptively for each individual drug and overall for those subjects who had dose reduction during treatment period.

Median time to first dose reduction with 95% CI will also be estimated based on Kaplan-Meier method for all the treated subjects. Subjects who did not have dose reductions during treatment period will be censored at the date of last dose.

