For subjects in the 14-mg QD (+everolimus 5 mg) arm, if there are no intolerable Grade 2 or any \geq Grade 3 TEAEs that require dose reduction in the first 28-day cycle (ie, the first 4 weeks of treatment), lenvatinib dose will be escalated to 18 mg QD (+everolimus 5 mg). See the Interactive Voice and Web Response System (IxRS) Manual and revised Pharmacy Manual for further instructions.

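### SAP 5.6.2.3, read with its own definition of interruption, backdates the first dose reduction to any earlier hold resumed at full dose, and leaves a hold followed by a higher dose unclassified

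*SAP*

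**What the plan says.** SAP 5.6.2.3 sets these rules:

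- **Interruption.** The definition is restrictive: "Dose interruption only refers to the scenario that the dose levels or dosing frequencies before and after interruption period" are equal, the interruption period being the stretch at zero dose.
- **Hold followed by a lower dose.** "If the dose level after dose interruption period was reduced from the dose level before the interruption period, it should be counted as dose reduction". Such a hold no longer counts among the interruptions. For the example 18-0-14 mg, "the dose reduction date should be the date of dose=0".
- **Hold followed by a permanent stop.** This is a discontinuation.
- **Time to first reduction.** It runs from first dose to the first reduction or, alternatively, to the "date of first dose interruption for those subjects who had dose interruption first and then followed by dose reduction".
- **Summaries.** The time is described for each drug and overall among subjects who had a reduction. In addition: "Median time to first dose reduction with 95% CI will also be estimated based on Kaplan-Meier method for all the treated subjects". Subjects without a reduction are censored at last dose.

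Protocol 9.4.1 adds a planned step in the 14-mg arm only. If Cycle 1 brings no qualifying TEAE that requires dose reduction, "lenvatinib dose will be escalated to 18 mg QD". Protocol 7.3 places this on Day 1 of Cycle 2.

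**The concern.** The 18-0-14 pattern is already a reduction dated to the first zero-dose day, so it needs no second rule. If interruption keeps its defined meaning, the alternative date can apply only to a hold resumed at full dose, and nothing requires that hold to lead to the reduction. An early hold for one reason then supplies the date of a reduction made months later for another.

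It also makes the event time depend on the future. Two subjects with the same hold on the same day are treated differently: one has an event that day because a reduction came later, the other has no event and is censored at last dose. A Kaplan-Meier estimate built this way does not describe time to first reduction.

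The definitions also leave a gap. Holds followed by the same dose, a lower dose or a permanent stop are classified; a hold followed by a higher dose is not, although the 14-mg arm has a planned increase.

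At stake is a descriptive tolerability summary. Protocol 9.7.1.8 asks for time to first dose reduction, and Protocol 9.7.1.6.1 bases the dosing decision on the totality of safety and efficacy data.

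**Working it through.** The plan gives no figure here to reproduce. The check applies the rules to hypothetical dose histories and then sizes the shift under stated assumptions.

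**1. Dose histories, first dose on day 1**

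| History | SAP classification | First reduction, literal SAP | First actual reduction |
|---|---|---|---|
| 18, 0 from day 21, then 14 | 1 reduction | day 21 | day 21 |
| 18, 0 from day 21, 18 from day 28, 14 from day 100 | 1 interruption, 1 reduction | day 21 | day 100 |
| 18, 0 from day 21, 18 from day 28, no later change | 1 interruption | none, censored at last dose | none |
| Everolimus 5, 0 from day 21, 5 from day 28, 0 from day 84, then every other day | 1 interruption, 1 reduction | day 21 | day 84 |
| 14, 0 from day 25, 18 from day 32 | neither | none | none |
| 14, 0 from day 15, 14 from day 20, 18 from day 29 | 1 interruption | none | none |

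The alternative date changes nothing in row 1, the pattern it might have been written for. It changes rows 2 and 4. The number of reductions is the same under either dating.

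**2. Where full-dose restarts arise**

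- *Everolimus.* Under Protocol Table 2 (9.4.2), a first intolerable Grade 2 or Grade 3 toxicity interrupts both drugs; lenvatinib drops one level and everolimus resumes at its previous dose. At a second or third occurrence, everolimus may be reduced for Grade 3 toxicity. Row 4 is therefore an ordinary pathway.
- *Lenvatinib.* Table 2 sends toxicity holds to a lower dose (row 1). Full-dose restarts come from Grade 2 non-infectious pneumonitis (9.4.2.5) or may follow surgical breaks (9.4.8.2), so they should be less common.

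**3. Size among reducers**

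Assumptions: time to first reduction is exponential with rate λ; a share q of reducers had an earlier full-dose hold; that hold falls uniformly between first dose and the reduction. With x = λs and E1 the exponential integral, the probability that the SAP time exceeds s is

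exp(−x) − q · x · E1(x).

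Setting this to 0.5 gives the median; without backdating, x = ln 2 = 0.6931. For q = 0.5, x = 0.4452: 0.6407 − 0.5 × 0.4452 × 0.6322 = 0.500, and 0.4452 / 0.6931 = 0.642, or 36% shorter.

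| Share of reducers affected | x at median | Shortening (formula) | 42-day median becomes (simulated) | 84-day median becomes (simulated) |
|---|---|---|---|---|
| 10% | 0.6408 | 8% | 38.7 | 77.7 |
| 20% | 0.5893 | 15% | 35.7 | 71.4 |
| 30% | 0.5391 | 22% | 32.8 | 65.6 |
| 50% | 0.4452 | 36% | 27.0 | 54.0 |

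Under these assumptions the percentage does not depend on the true median.

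**4. Size in the Kaplan-Meier analysis**

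A second model takes full-dose interruption, reduction and end of treatment as independent exponentials, with median time on treatment 40 weeks and true median time to reduction 16 weeks. If 9% of reducers are backdated, the Kaplan-Meier median falls from 16 to about 14.8 weeks; if 42% are, to about 10.0 weeks. These shares are assumptions too.

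**5. The 14-0-18 gap**

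It needs a lenvatinib hold spanning Cycle 2 Day 1 for a reason that did not require dose reduction. A hold resumed at 14 mg before the step is counted correctly (last row of the first table). Protocol 9.4.2 also lets a mistakenly lowered dose be raised with sponsor approval in either arm, so an 18-mg-arm subject cut to 14 in error, held and restored to 18 has an unclassified hold as well.

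**The case against.** The strongest reply is that the SAP does not keep to its own definition. The same section speaks of an interruption period before a lower dose, and of permanent discontinuation after an interruption; neither is a same-dose break. The disputed clause may simply restate the 18-0-14 dating rule, in which case nothing is backdated. Derivation rules also sit in separate documents (SAP section 9) that are not available here. This stands as a plausible account of intent. It does not rescue the wording: on that reading the clause is redundant and contradicts the definition just above it, and two programmers could defensibly derive different medians.

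Second, the practical reach may be small. Lenvatinib toxicity holds normally end in a lower dose. For everolimus, Protocol 7.1 reports that in the combination arm of Study 205, 76.5% of subjects had interruptions due to AEs but only 2.0% had dose reductions. At that rate there would be about 0.02 × 169 ≈ 3 everolimus reducers per arm, and the Kaplan-Meier median would not be reached under either rule. Those figures do not give the share of reducers with an earlier full-dose hold, and they come from another study. They do argue against assuming a large effect.

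Third, a reader might infer that the dose-change tables are wrong in general, that one error falls only on the 14-mg arm and favours it, or that the main tolerability comparison is compromised. The documents do not support this. Reduction counts are unchanged. A corrected mistaken decrease can leave a hold unclassified in either arm. The holds missed in the 14-mg arm are largely those, such as surgery, that say little about tolerability, and zero-dose days still lower dose intensity (SAP 5.6.2.2). The tolerability claim rests on the primary safety endpoint. Time to first dose reduction is not a listed endpoint and has no planned test.

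**Conclusion.** The point holds as a defect of definition in a descriptive exposure summary. Read with its own definition of interruption, SAP 5.6.2.3 dates the first reduction to any earlier hold resumed at full dose, while the same hold without a later reduction leads to censoring at last dose. If only the hold directly before a lower dose was meant, the clause is redundant and conflicts with the definition. Either way it should be corrected.

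The shift is always towards an earlier reduction. Its size depends on how often full-dose holds precede reductions, which the documents do not give: about 8% to 36% among reducers for shares of 10% to 50%, under the stated distributions. A higher share is most plausible for everolimus, because the protocol restarts it at the same dose after a first toxicity. A between-arm distortion would need the arms to differ in this share, and nothing in the documents shows that they do.

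The unclassified 14-0-18 hold is a smaller matter. Interruption counts may be slightly low, mainly in the 14-mg arm because only that arm has a planned escalation. Subjects with reductions, reductions per subject, the primary endpoints, alpha and sample size are unaffected.

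**What to change.** In SAP 5.6.2.3:

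1. Delete the alternative date based on the first interruption, or limit it to the zero-dose period that leads directly to resumption at a lower dose. Row 2 of the dose-history table then gives day 100 and row 4 day 84; row 1 stays at day 21.
2. Define an interruption as a zero-dose period followed by resumption at the same or a higher dose. A 14-0-18 mg sequence then counts as one interruption, with the planned escalation recorded separately.

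The cost is two sentences in the SAP and matching changes in the exposure dataset specification. The dosing records already hold the data, and no other analysis changes.
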